#### **4.9.1.3 Adjustments for Covariates**

Adjustment for the following covariates will be considered: baseline value, disease duration (<2 years,  $\geq$ =2 years), weight, age, and sex.

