**Table 4 Interim and Final Deliveries**

Analysis	Timing	Deliverable	Unblinded Team	Main Objective
Interim 1	90 subjects complete Week 4	PAREXEL: ADAM datasets and demography table (see Table 5 )  GSK: efficacy displays (see Table 5 ) and PK if required	Unblinded PAREXEL programmers, GSK lead and QC statistician, DRC	Evaluate whether to stop the study based on: • Dose response relationship at Week 4 (i.e., if all doses have $> -0.4$ point difference over placebo using the Week 4 dose response model estimates for change from baseline in DAS28(CRP)).
Interim 2	90 subjects complete Week 12	PAREXEL: ADAM datasets and demography table (see Table 5 )  GSK: efficacy displays (see Table 5 ) and PK if required	Unblinded PAREXEL programmers, GSK lead and QC statistician, DRC	Evaluate whether to stop the study based on: • Dose response relationship at Week 12 (i.e., if all doses have $> -1.0$ point difference over placebo using the Week 12 dose response model estimates for the change from baseline in DAS28(CRP)). • Dose response relationship and predictive probabilities (i.e., if at least one dose $\leq -1.0$ over placebo using the Week 12 dose response model estimates but the predictive probabilities of seeing a 25% difference at Week 24 in DAS28(CRP) remission is $<30\%$ ). Evaluate whether to drop a treatment arm based on: • An individual dose with $> -1.0$ point difference over placebo using the Week 12 dose response model estimates for change from

				baseline in DAS28(CRP).
Week 24	All subjects complete Week 24 visit	PAREXEL: Unblinded Week 24 displays.	PAREXEL lead and QC biostatisticians and programmers, GSK.	Unblinded primary/secondary analyses, safety and PK.
Final	All subjects complete the study (follow-up visit at Week 62)	PAREXEL: All unblinded displays, including exploratory endpoints, SDTM and ADAM datasets.	PAREXEL lead and QC biostatisticians and programmers, GSK.	Final reporting for Study 201755.

Unblinded interim analyses will be conducted when 90 subjects (i.e. on average 15 per arm) have completed 4 and 12 weeks of treatment. Efficacy analysis for the interim analyses will not be analysed by PAREXEL but by GSK. These interim analyses will be aligned with the unblinded safety review of the DRC where possible, see section [4.10.11](#).

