### DAS28(CRP) change from baseline

DAS28(CRP) scores and changes from baseline will be summarised for each visit. The mean change from baseline in DAS28(CRP) score and 95% CI will be plotted by randomised treatment group.

For change from baseline in DAS28(CRP) score, a mixed model repeated measures (MMRM) analysis will be conducted including all weeks up through Week 12. For the first interim the analysis will subset on those subjects with Week 12 DAS28(CRP) scores. The model will be fitted with fixed effects for randomised treatment group, visit, treatment by visit interaction and baseline DAS28(CRP), and visit within subject as a repeated effect. The covariance will initially be specified as unstructured covariance matrix. If SAS® gives a non-convergence warning, the

results will not be used – instead the warning will be stored and the spatial power law structure will be used in order to reduce the number of parameters to be estimated.

The point estimates and corresponding 95% CI for the treatment differences will be constructed using the residual error from the model; these estimates will be summarised and plotted for each randomised treatment group comparison over time.

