### **Dose-Response at Weeks 4, 8 and 12**

A plot of the mean change from baseline in DAS28(CRP) score and 95% CI versus dose will be provided separately for each of Weeks 4, 8 and 12.

The dose-response relationship for the change from baseline in DAS28(CRP) score will be evaluated at Week 4, 8 and 12 using a three parameter  $E_{max}$  model of the form:

$$Y = E_0 + E_{max} * [Di / \{ ED_{50} + Di \}]$$

where  $E_0$  is the placebo effect,  $E_{max}$  is the maximum achievable effect above placebo,  $ED_{50}$  is the dose at half  $E_{max}$  and  $Di$  are doses =0, 22.5, 45, 90, 135 and 180 mg.  $Y$  is a measure of change from baseline in DAS28(CRP) continuous score.

If this Emax model is not applicable then additional models will be investigated, including a four parameter  $E_{max}$  model with a slope factor  $B > 0$ :

$$Y = E_0 + E_{max} * [Di^B / \{ ED_{50}^B + Di^B \}]$$

and the model with the expected response as a linear function of dose:

$$Y = E_0 + E_1 * Di$$

Each of the models will be fitted to the data and their fit compared using the Akaike information criteria (AIC), where the model with the lowest AIC will be the primary model for inference. The additional models will be considered secondary models, and will not be utilised unless issues arise with the residual checks on the primary model. Distributional assumptions will be assessed by examining plots of the residuals from the primary model.

The final model parameters for the dose-response will be summarised; a plot of the dose-response relationship will be provided. The chosen models might differ between Week 4, 8 and 12. SAS outputs of all secondary models will be shown.

## Posterior Probabilities at Week 12

In addition to assessing the dose response model for the DAS28(CRP) change from baseline data at Weeks 4, 8 and 12, the posterior distribution for the Week 12 change from baseline in DAS28(CRP) will be calculated.

This will be derived assuming the data follow a normal distribution with mean  $\mu_i$  and precision  $\tau_i$  (where  $i=0$  is the placebo group and  $i=1-5$  are the treatment groups) and non-informative prior distributions for  $\mu$  and  $\tau$ :

$$\mu_i \sim N(0, 10^{-2})$$

$$\tau_i \sim Ga(0.001, 0.001)$$

Given the small number of subjects expected with Week 12 data at the first interim analyses, alternative prior distributions for  $\tau$  may be investigated.

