**Table 6 Summaries and Analyses for Primary and Secondary Endpoints**

	Summary Statistics						Statistical Analyses							
	Observed	CfB/Proportion			Subgroups	Dose Response			MMRM/Logistic			Survival (Time to 1st)		
	T	T	F	L	T	T	F	O	T	F	O	T	F	O
DAS28(CRP) score	Y	Y	Y	Y	Y1	Y at Week 24	Y	Y	Y	Y	Y			
DAS28(CRP) remission		Y		Y	Y1	Optional at Week 24	Y	Y	Y		Y	Y	Y	Y
DAS28(CRP) EULAR response		Y		Y	Y1				Y		Y			
ACR20/50/70		Y		Y	Y1				Y		Y			
Components: TJC28, TJC68, SJC28, SJC66, CRP, PtGA, PhGA	Y	Y		Y					Y		Y			
Index- and Boolean-based ACR/EULAR remission		Y			Y1				Y		Y			
CDAI remission		Y							Y		Y			
SDAI, CDAI scores	Y	Y							Y	Y	Y			
HAQ-DI score	Y	Y							Y	Y	Y			
HAQ-DI pain severity				Y										
Pain score	Y	Y							Y	Y	Y			
SF-36 physical, mental and domain scores	Y	Y							Y	Y	Y			
FACIT-Fatigue	Y	Y		Y					Y	Y	Y			
BFI Question 3	Y	Y		Y					Y	Y	Y			

CfB=Change from baseline; T=table; F=figure; L=listing; O=supportive analysis SAS output.  
1 Disease duration ((<2 years,  $\geq$ 2 years), gender.

For plots of change from baseline endpoints, the mean change from baseline and 95% CI will be plotted by randomised treatment group.

Plots of Mean and 95% CI of Change from Baseline in DAS28(CRP) at Each Visit will be created.

Subject profile plots of DAS28 score at each visit will be produced.

Dose response analyses for change from baseline in DAS28(CRP) will be conducted after visual inspection of the mean and 95% CI plots and using the final model from the second interim analysis as a starting point for the dose response modelling. The Week 24 primary analysis model will be fitted without covariate terms. A plot of the residuals versus predicted values will be examined to assess distributional assumptions. If additional models are fit, the smallest AIC will be used to help identify the best fitting model. Covariates from the Week 24 primary analysis of DAS28(CRP) remission may be added to the model in a sensitivity analysis. Model results from the sensitivity analysis will be provided in the corresponding listing.

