For binary endpoints with repeated measures over time, Generalized Estimating Equations (GEE) methodology will be used to take correlation among subject-level responses over time into account. The model will include data from all assessment points from Week 1 to Week 62. Due to only few expected subjects with remission in some randomised treatment groups (especially placebo) only standard errors and resulting confidence intervals will be adjusted. To this end an independent working correlation structure will be assumed and standard errors will be calculated based on the empirical sandwich covariance estimate (default setting for PROC GENMOD in SAS) (Stokes, Davis, & Koch, 2012).

For the primary analysis of DAS28(CRP) remission at Week 24, the GEE model will include terms for randomised treatment group, baseline DAS28(CRP), visit and interaction terms for treatment group-by-visit and baseline-by-visit. A sensitivity analysis including covariates age, gender, weight and disease duration (<2 years,  $\geq 2$  years) will be considered by adding covariate terms to the repeated measures model one at a time along with the covariate-by-treatment group interaction term. If the interaction term is not significant at  $\alpha=0.10$  it will be removed from the model. Likewise, if the covariate term is not significant at  $\alpha=0.10$  it will be removed from the model. Other covariates will be tested in a similar manner.

Survival analyses (time to event analyses) will be conducted for the final analysis using Kaplan-Meier methods, comparing each GSK3196165 dose to placebo. Between-group differences will be analysed using the log-rank statistic. Median time to remission will be presented for each randomised treatment group. Kaplan-Meier plots of the time to remission will be presented. Subjects who withdraw from the study are censored at the time of withdrawal. All other subjects are censored at the end of the study.

In addition to summaries of the individual components of composite endpoints, numbers and percentages of subjects meeting the following criteria will be presented:

- TJC68  $\leq 1$
- SJC66  $\leq 1$
- CRP  $\leq 1\text{mg/dl}$
- PtGA  $\leq 10$
- SDAI  $\leq 3.3$

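### The dose-response models for change in DAS28(CRP) leave out baseline DAS28(CRP), which the MMRM and GEE include, and so give up some precision in the estimates that Table 4 compares with its stop and drop thresholds.

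*SAP*

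**What the plan says.** **Interims (SAP 4.9.2.1, subsection on dose response).** The model is stated thus: "The dose-response relationship for the change from baseline in DAS28(CRP) score will be evaluated at Week 4, 8 and 12 using a three parameter" (the sentence goes on to name Emax). The equation has a placebo level, a maximum effect, an ED50 and dose. The 4-parameter and linear alternatives are also functions of dose alone.

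**Week 24 (SAP 4.9.2.2, dose-response paragraph below Table 6).** The fit starts from the Interim 2 model. "The Week 24 primary analysis model will be fitted without covariate terms". Adjustment appears only as an option: "Covariates from the Week 24 primary analysis of DAS28(CRP) remission may be added to the model in a sensitivity analysis", with those results going to a listing.

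**Other models in the same SAP.** The interim MMRM of the same endpoint includes baseline (SAP 4.9.2.1: "fixed effects for randomised treatment group, visit, treatment by visit interaction and baseline DAS28(CRP"). For the primary remission analysis, "the GEE model will include terms for randomised treatment group, baseline DAS28(CRP), visit and interaction terms for treatment group-by-visit and baseline-by-visit". SAP 4.9.1.3 is general: "Adjustment for the following covariates will be considered: baseline value, disease duration" and other variables. It assigns none of them to the dose-response fits.

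**Decision rules (SAP Table 4).** Interim 1 may stop the study if every dose falls short of a -0.4 "point difference over placebo using the Week 4 dose response model estimates". Interim 2 uses -1.0 from the Week 12 dose-response model, both for stopping the study (all doses short) and for dropping single arms. Each interim takes place at 90 subjects, about 15 per arm.

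**The concern.** Baseline DAS28(CRP) is collected on everyone and the SAP already treats it as the standard adjustment variable. It is missing from the one family of models whose estimates are set against numerical stop and drop thresholds, at the smallest sample size in the trial. The SAP gives no reason. Protocol 9.4.2 also makes Week 12 dose response the key secondary analysis.

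Using change from baseline as the response does not remove the influence of baseline. If baseline and change are correlated within arm, part of the scatter in the dose-minus-placebo estimate is explainable and is left in. At stake is how often a dose that truly meets -1.0 is judged to miss it, and how precisely the curve is described at Week 24.

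**Working it through.** **Inputs from the documents.** E0 = -1.0, Emax = -1.65, SD 1.0, 15 per arm, six arms (SAP 4.13.2); thresholds from SAP Table 4. ED50 is not stated. From the tabled 90 mg mean, (2.1 - 1.0)/1.65 = 0.667 = 90/(ED50 + 90), so ED50 = 45 mg. The true differences from placebo in the plan's table are then -0.54, -0.83, -1.10, -1.24 and -1.32 for 22.5 to 180 mg. So 90, 135 and 180 mg truly meet -1.0; 22.5 and 45 mg do not.

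**Assumption.** The within-arm correlation rho between baseline and change is not in the documents. I use 0 to 0.6 (absolute value).

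**The plan's own figure first.** Unadjusted Emax fits were simulated (least squares, ED50 profiled over 1 to 1000 mg, 4,000 to 6,000 runs), reading precision within 0.45 as a 95% CI half-width below 0.45. This gives 90.7% at 22.5 mg, against 90.4% stated. The other doses are close but not exact: 100% against 97.9%, 98.8% and 98.9% at 45, 90 and 135 mg, and 88.8% against 95% at 180 mg (92% without fits at the ED50 boundary). Reading it instead as distance of the estimate from the truth gives 98.2% at 22.5 mg, which does not match.

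**Adding baseline.** The model becomes Y = E0 + b × (baseline - mean baseline) + dose term. Residual variance is multiplied by (1 - rho²), less the small cost of estimating b. Equivalent subjects per arm = 15/(1 - rho²); for rho = 0.5, 15/0.75 = 20.0.

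**Results at 15 per arm, unadjusted → adjusted.** The last two columns apply only the -1.0 comparison.

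| rho | Equivalent n per arm | SD, 135 mg minus placebo | 22.5 mg half-width < 0.45 | 90 mg wrongly dropped | All doses short (study stop) |
|---|---|---|---|---|---|
| 0 | 15.0 | 0.296 → 0.299 | 90.8% → 90.0% | 37.5% → 37.4% | 12.9% → 12.8% |
| 0.2 | 15.6 | 0.297 → 0.293 | 91.2% → 93.1% | 38.1% → 37.2% | 12.5% → 12.4% |
| 0.3 | 16.5 | 0.297 → 0.286 | 91.5% → 95.7% | 38.2% → 37.0% | 12.1% → 12.0% |
| 0.4 | 17.9 | 0.297 → 0.275 | 91.6% → 98.3% | 37.9% → 36.5% | 12.3% → 11.3% |
| 0.5 | 20.0 | 0.296 → 0.260 | 91.4% → 99.8% | 37.8% → 35.7% | 12.5% → 10.0% |
| 0.6 | 23.4 | 0.296 → 0.241 | 91.7% → 100% | 37.6% → 34.6% | 12.3% → 8.6% |

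The SD falls by about 1%, 4%, 7%, 12% and 19% for rho 0.2 to 0.6, and rises by about 1% at zero. For 135 mg the wrong-drop rate goes from about 20% to 19% (rho 0.3), 17% (0.5) and 16% (0.6). Small differences between rows in the unadjusted figures are simulation noise.

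**Week 24.** At 35 per arm the SD of the same contrast falls from about 0.195 to 0.187, 0.169 and 0.156 for rho 0.3, 0.5 and 0.6: much the same proportions.

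**Not computed.** The plan gives no assumed Week 4 curve, so the effect on the -0.4 rule at Interim 1 cannot be sized.

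**The case against.** **Decisions hardly move, and the gain may be near zero.** This largely stands. Wrong-decision rates change by about 0 to 4 points, because the assumed 90 and 135 mg effects lie only 0.10 and 0.24 beyond -1.0 and adjustment does not alter that. Nor is rho known. If baseline and follow-up had equal variances, rho = √((1 - r)/2) in size, which is 0.50 to 0.39 for a between-visit correlation r of 0.5 to 0.7. With assumed SDs of 0.9 at baseline and 1.2 at follow-up and r = 0.6, the covariance of baseline with change is 0.648 - 0.810 = -0.162, the SD of change is √0.954 = 0.977, and rho is 0.162/(0.9 × 0.977) = 0.18. The gain is then under 2% in SD. The planning SD of 1.0 is also not said to be raw or adjusted.

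**The committee is not without adjusted estimates.** True: SAP Table 5 sends the baseline-adjusted MMRM to the DRC at both interims. It does not feed the Table 4 thresholds, though, and the SAP does not say which estimate prevails if the two disagree.

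**Stronger readings that the documents do not support.**
- *The Week 24 fit fixes the Phase 3 dose.* No such rule is written. SAP 3.1.4 ties dose selection to the interim analyses.
- *The Emax fit alone decides the interims.* Interim 2 also uses predictive probabilities of remission, and further criteria sit in the DRC Statistical Guidance Document, which is not available here.
- *The sentence excluding covariates governs the interims.* It concerns Week 24. The interim point rests on the dose-only equations.
- *Baseline imbalance biases the estimates.* Randomisation keeps them unbiased, and only the residual slope times the imbalance enters a change score.

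**Conclusion.** The point holds as a loss of efficiency, not as an error of validity. The omission is plain in the text, and so is the contrast with the MMRM and GEE. Table 4 does read its dose-response thresholds off the unadjusted fits. The direction is secure for any appreciable correlation; the size is not.

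For rho between 0.2 and 0.6, adjustment is worth about 0.6 to 8.4 extra subjects per arm at the interims, against a cost of about 1% in SD if rho is zero. These figures assume the plan's Emax curve, SD 1.0 taken as the raw value, a linear baseline effect common to all arms, and complete data. They cover the dose-response rule alone, not the full Interim 2 decision. It is worth changing because it costs almost nothing, not because the interim decisions would otherwise be unsound.

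**What to change.** In SAP 4.9.2.1 and 4.9.2.2, prespecify centred baseline DAS28(CRP) as an additive linear term in every candidate dose-response model (3-parameter Emax, 4-parameter Emax, linear) at Interim 1, Interim 2, Week 24 and the final analysis. With the term in all candidates, the AIC comparison stays like for like. State in Table 4 that the dose-minus-placebo estimates come from this fit. The term is additive, so the difference from placebo remains a function of dose alone and the -0.4 and -1.0 thresholds keep their meaning. Keep the unadjusted fit as the sensitivity analysis, and record the change in SAP 4.14, since protocol 9.4.2 shows the dose-only equation.

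The cost is one parameter per model and SAP wording. No new data are needed.

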#### **4.9.1.2 Multi-center Studies**

This study will randomise 210 subjects into 6 treatment arms, so that on average only 35 subjects per arm will be enrolled (although some arms may have larger patient numbers if inferior arms are dropped at the interim analyses). The number of sites (centres) may be roughly around 70, so that an adjustment of the analyses by centre will not be feasible.

For all analyses all sites, countries and regions will be pooled.

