Markov-Chain-Monte-Carlo (MCMC) methods in SAS® will be used to derive the posterior distributions for each randomised treatment group and to also derive the distribution of the difference between each treatment group and the placebo group. From this difference distribution the posterior probability that the treatment difference between each active dose and placebo being  $> 1$  will be calculated.

Decision criteria for stopping the study after Interim Analysis 1 are specified in the DRC Statistical Guidance Document.

## DAS28 (CRP) remission rates at Week 24

The number and percentage of subjects achieving DAS28(CRP) remission ( $DAS28(CRP) < 2.6$ ) will be summarised for each randomised treatment group and visit. Fisher's exact test will be used to test for randomised treatment group differences at Week 24 in the proportion of subjects achieving remission for each GSK3196165 treatment group versus placebo.

## Predictive Probabilities at Week 24

The proportion of subjects with available DAS28(CRP) remission data at week 24 at the interim analysis will only be summarised using counts and proportions. This is because only a low number of subjects with week 24 data are expected at the week 12 interim analysis.

In addition, the predictive probability that the difference in DAS28(CRP) remission between each dose and placebo at the end of the study is  $> 15\%$  and  $> 25\%$ , given the results at the interim analysis and the prior information will be calculated using the procedure described below.

The following information will be available at the interim:

- $l_i$  = number of subjects that have reached week 24 in each randomised treatment group  $i$ ,  $i=0, \dots, 5$  ( $i=0$  being the placebo arm and  $i=1-5$  being the 5 treatment groups, with  $i=1$  being 22.5mg)
- $x_i$  = observed number of subjects in DAS28 remission at week 24 in each randomised treatment group  $i$ ,  $i=0, \dots, 5$  ( $i=0$  being the placebo arm and  $i=1-5$  being the 5 treatment groups, with  $i=1$  being 22.5mg)

Our prior Beta distribution on the remission rate in each randomised treatment group:  
 $\pi_i \sim \text{Beta}(\alpha_i^0, \beta_i^0)$

- Placebo:  $\alpha_0^0 = 9$ ,  $\beta_0^0 = 91$ , so the prior mean remission rate is 9%, and the 95th interval is (4%, 15%)
- Active group:  $\alpha_i^0 = 1$ ,  $\beta_i^0 = 1$ , equivalent to a uniform distribution (non informative). This will apply to all active groups ( $i=1$  to 5)

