Dose response analyses for DAS28(CRP) remission might be done as an ad-hoc analysis. MMRM analyses will be conducted similarly to interim analysis methods. Distributional assumptions underlying the model used for analysis will be examined by obtaining a normal probability plot of the residuals and a plot of the residuals versus the predicted values (i.e. checking the normality assumption and constant variance assumption of the model respectively) to gain confidence that the model assumptions are reasonable. If there are any departures from the distributional assumptions, alternative models may be explored using appropriate transformed data

For change from baseline in DAS28(CRP), if the dropout rate is  $\geq 10\%$  for the Week 24 or Week 52 analysis, further sensitivity analyses using multiple imputation as explained in section 4.5.2.3 may be conducted as ad-hoc analyses. In order to assess subgroup effects, additional analyses will be conducted with subgroup and subgroup interaction with treatment as covariates.

For DAS28(CRP) remission, subjects with missing data as defined in Section 3.2.1 will be imputed as non-responders as described in Section 4.5.2.1. Differences in remission rates between each active arm and placebo will be summarised at each visit through Week 52. 95% CI for the differences will be constructed using their asymptotic standard errors (asymptotic Wald confidence limits) without continuity correction.

Logistic regression models will have fixed effects for randomised treatment group and baseline value. The odds ratios, 95% CI and p-values for the comparison of each GSK3196165 treatment group versus placebo at key time points will be presented. Covariates age, gender, weight and disease duration ( $<2$  years,  $\geq 2$  years) will be considered in alignment with the results of the primary analysis model.

For ACR response, baseline values of TJC68 and SJC66 will be considered as fixed effects, as a baseline value of ACR response does not exist.

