#### **4.13.1 Primary Analysis**

The sample size for the primary analysis and hence the overall sample size for the study is based on detecting a 30% difference from placebo in the proportion of subjects in remission (DAS28 score <2.6) at Week 24 of the 52 week double-blind treatment period for each GSK3196165 dose.

Using a Fisher's exact test, a sample size of 35 subjects per arm will provide approximately 90% power to detect a difference of 30% in the proportion of subjects in remission between each GSK3196165 dose (33%) and placebo (3%) at the two-sided  $\alpha=0.05$  level at 24 weeks. The placebo rate of 3% is based on a literature review of current therapies presenting DAS28(CRP) remission results. No adjustments will be made to the sample size to account for the multiple doses in this Phase 2 study.

The least significant difference this sample size will detect is an approximate 17% difference from placebo.

The sample size will not be increased to account for dropouts and all dropouts within the treatment period will be classed as non-remitters for the primary analysis.

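### Wald limits for the DAS28(CRP) remission differences fall short of 95% coverage at the sparse counts the SAP plans for, mainly through upper limits set too low

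*SAP*

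**What the plan says.** SAP 4.9.2.2 plans differences in DAS28(CRP) remission for every active arm: "Differences in remission rates between each active arm and placebo will be summarised at each visit through Week 52". For their limits it states: "95% CI for the differences will be constructed using their asymptotic standard errors (asymptotic Wald confidence limits) without continuity correction". Sections 4.9.3.1 (sustained remission) and 4.9.3.2 (major clinical response) refer back to the same methods, minus the GEE part, and so take over this interval.

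The same section expects sparse data. In explaining its GEE covariance choice it gives the reason "Due to only few expected subjects with remission in some randomised treatment groups (especially placebo").

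The planning figures agree with that. SAP 4.13.1 says "a sample size of 35 subjects per arm will provide approximately 90% power" for a "difference of 30% in the proportion of subjects in remission between each GSK3196165 dose (33%) and placebo (3%) at the two-sided" 0.05 level. The interim prior for placebo (SAP 4.9.2.1) has mean 9%. Some active arms may end below 35. Table 4 allows an arm to be dropped at Interim 2, and the text below it sets the timing: "Unblinded interim analyses will be conducted when 90 subjects (i.e. on average 15 per arm) have completed 4 and 12 weeks of treatment". Placebo continues and recruitment is not paused (SAP 3.1.4).

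**The concern.** The Wald interval estimates its standard error from the observed proportions. When an arm has no remitters, that arm contributes no variance, and the interval is too narrow when the data are thinnest. At a 3% placebo rate, 35 subjects yield no remitter with probability 0.97^35 = 34%.

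The risk difference is the directly readable form of the primary endpoint in a trial meant to choose Phase 3 doses. An upper limit that is too low makes a dose with few observed remitters look more firmly ruled out than the data allow. An interval of zero width claims certainty where there is almost no information.

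**Working it through.** **Inputs.** 35 per arm, placebo 3%, active 33%, two-sided 0.05 (SAP 4.13.1). Second placebo rate 9% (interim prior, SAP 4.9.2.1). 210 subjects in six arms (SAP 4.9.1.2). *Assumption:* a dropped arm ends with 15 to 25 subjects. The SAP gives only the interim average of 15 completers per arm, and recruitment continues, so 15 is a lower bound. With k arms stopped at m subjects and the rest shared equally, each remaining arm has (210 - k·m)/(6 - k): one arm stopped at 15 gives 39, two give 45, and three stopped at 20 give 50. I used 35 to 50 for placebo.

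**The plan's own figure.** Enumerating all 36 × 36 outcomes with the two-sided Fisher test gives 90.9% power at 3% against 33%, which agrees with the stated 90%. All nine cells of SAP Table 11 come out within 2 points.

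**Intervals.** With observed proportions p1, p0 and d = p1 - p0:
- Wald: d ± 1.96·√[p1(1-p1)/n1 + p0(1-p0)/n0].
- Newcombe: from d - √[(p1-l1)² + (u0-p0)²] to d + √[(u1-p1)² + (p0-l0)²], where l and u are Wilson score limits for each arm.

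**Coverage** is the sum of Bin(x; n1, π1)·Bin(y; n0, π0) over outcomes whose interval contains π1 - π0. Wald coverage in %, true placebo rate 3%:

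| Active n / placebo n | active 10% | 15% | 20% | 33% |
|---|---|---|---|---|
| 35 / 35 | 93.7 | 94.1 | 92.9 | 93.5 |
| 25 / 35 | 91.2 | 89.1 | 92.8 | 93.6 |
| 20 / 35 | 87.2 | 91.2 | 91.3 | 93.0 |
| 15 / 35 | 78.8 | 90.0 | 91.3 | 91.5 |
| 15 / 50 | 78.6 | 89.8 | 89.4 | 90.5 |

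Newcombe coverage in these cells lies between 95% and 99%. At active rates below 10% Wald is lower still: 87.8% at 35/35 with 6%, and 75.3% at 15/35 with 9%.

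**Other rates.** With placebo at 9%, 35/35 gives about 94-95% for active rates of 9-45%; 15/35 with both rates at 9% gives 89.7%. With both rates at 3%, Wald over-covers: 98.6% at 35/35.

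**Direction of the misses.** At 35/35, 3% against 10-33%, the upper limit lies below the true difference in 4.3-5.4% of trials and the lower limit lies above it in 0.9-2.2%; each should be 2.5%. At 15/35, 3% against 9%, the split is 24.3% and 0.4%. The 24.3% is the chance of no active remitter, 0.91^15. With 0/15 against 1/35, Wald runs from -8.4 to +2.7 points and misses the true +6; Newcombe runs from -14.5 to +17.7.

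**Zero width.** With 0/35 in both arms the Wald standard error is 0 and the interval is [0, 0]. The Wilson upper limit is 1.96²/(35 + 1.96²) = 9.9%, so Newcombe gives ±9.9 points. If both true rates are 3%, this outcome has probability 0.97^70 = 12%.

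**At the planned effect little changes.** For 12/35 against 1/35, d = 31.4 points and the standard error is √(0.00644 + 0.00079) = 0.0850, so Wald gives 14.8 to 48.1. Wilson limits of 20.8-50.9% and 0.5-14.5% give Newcombe 13.6 to 48.2.

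**The case against.** The best defence is that little depends on this interval. The primary analysis is an odds ratio from a GEE logistic model with its own interval and p-value. Interim decisions use dose-response estimates and predictive probabilities. This is a Phase IIb study with no multiplicity adjustment. In full arms the shortfall at 10-33% is one to two points. All of that stands and limits the weight of the point.

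It also stands that the remark about few remitters explains the GEE choice, not the difference interval. I use it only as evidence of the counts the SAP expects. The 12% chance of a zero-width interval needs a dose with no effect.

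A reader might go further and infer that Wald limits will declare benefit where an exact test would not. The documents do not support that. No Fisher test is planned at Week 24; it is named for sample size and for interim displays. With full arms at 3% against 10-33% the lower limit errs less often than 2.5%. Newcombe also disagrees with Fisher, in 6-14% of trials at 3% against 10-20%. In small arms Wald excludes zero less often than Newcombe: 4.7% against 9.6% at 15/35, 3% against 10%.

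A reader might also take 15 as the final size of a dropped arm, or extend the criticism to all response differences. The first is an interim average of completers. For the second, the Wald sentence concerns DAS28(CRP) remission and reaches only sustained remission and major clinical response by reference.

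**Conclusion.** The point holds as a modest error in a supporting summary. With 35 per arm at the planning placebo rate the shortfall is about 1 to 2 points at active rates of 10-33%, and about 7 points at 6%. It becomes material for small arms with few remitters: about 79-94% coverage for 15-25 active against 35-50 placebo at active 10-33%, if dropped arms end at such sizes. The error is mainly one-sided and understates the upper end of plausible benefit.

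The figures rest on independent binomial counts with non-responder imputation, so that denominators stay at arm size. They take no account of selection from dropping arms on interim data. They say nothing against the primary test or the interim rules.

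**What to change.** In SAP 4.9.2.2, replace the Wald limits by Newcombe (hybrid score) or Miettinen-Nurminen limits for the DAS28(CRP) remission differences, and state that 4.9.3.1 and 4.9.3.2 use the same limits. Newcombe's lowest coverage for arms of 15-35 with placebo at 3% or 9% was 94.7%. Miettinen-Nurminen gave 94.4% at 35/35 (3% against 33%) and 94.6% at 15/35 (3% against 9%). Adding a continuity correction to Wald is not enough: it reaches 89.4% in that last case.

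The cost is one sentence and one analysis option, with no change to design, data or the primary test. Full-arm intervals will usually be slightly wider. The SAP allows SAS 9.2 or later, so the programmer should confirm that the version in use offers the chosen limits.
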